*** Identify the subgroups and provide a justification:**

Our clinic and therefore voice therapy approaches are for adult populations. Further, the developing larynx of children and adolescents is different from the adult larynx.

Therefore, it is not always appropriate to compare treatments and outcomes between pediatric and adult voice disordered populations.

8. **Describe the power analysis used and cite your method of statistical analysis.**

If a power analysis is not possible, thoroughly justify the sample size required

for the study, including appropriate literature citation (alternatively provide page reference in attached protocol):

Due to the pilot nature of the current study, we will use convenience sampling. Our clinic evaluates approximately 30 new patients each week. Behavioral voice disorders such as those included in the current research are approximately 60% of all new patient visits. Therefore, we do not anticipate difficulty recruiting our target N of 20 for this pilot investigation. A paired t-test will be used to assess whether VHI-10 improved significantly from baseline.

Research Activities

- * Provide a detailed description of all research activities (including screening and follow-up procedures) that will be performed for the purpose of this research study. This description of activities should be complete and of sufficient detail to permit an assessment of associated risks.**

Participants will be recruited from the University of Pittsburgh Voice Center.

Participants diagnosed with a voice disorder (including primary MTD, lesions, and atrophy) by a board certified speech language pathologist (SLP) will be the target population for this study.

Participants will age 18 and older and must state willingness to attend 4 sessions of voice therapy (standard of care for voice therapy for voice disorders) and attend a one-week follow-up research testing visit.

Participants will be assigned to a voice therapist (SLP) and scheduled for 4 sessions.

Patients will be given a facemask with a semi-occlusion (SOMask) for use in clinic and with a home practice program.

The therapy program is based on treatment program designed for a semi-occluded tube therapy found in the literature and conversation training therapy, a program developed by these investigators and validated at this institution (PRO15030497).

Each voice therapy session will last approximately 45 minutes and will consist of:

Review of vocal hygiene

For all exercises, instruct patient to:

- Breathe outside of mask, phonate into mask
- Abdominal breathing
- Relaxed upper body
- SOMask connected speech- topic of subject's choice
- Auditory and kinesthetic awareness of voice production
- Embedded basic training gesture
- Prosody training
- Negative practice- patient produces the "good" voice, alternating with the "bad" voice

Home program:

- 1 min of mask speech, 4x/day practice
- Record sessions on patient's smart phone for home practice
- Log sheet for homework practice

Baseline data to be collected will be extracted from the medical record.

Data collected at Baseline:

- VHI-10 (per usual clinical care)
- auditory perceptual analysis (per usual clinical care)
- Acoustic outcomes in vowels and speech- "we were away a year ago" (per usual clinical care)
- Aerodynamic outcomes (per usual clinical care)

Medical record information will be accessed to collect clinical information related to eligibility for this project, and to record voice outcome measure information (such as the VHI-10). This information will be collected by individuals involved in this research who have normal clinical access to this information or by the research coordinator who has been granted access through the Privacy Office.

All recruitment and enrollment will take place at UPMC Mercy. Voice therapy sessions will occur at Mercy, East, and Passavant and Bethel Park.

Data collected at follow-up:

- VHI-10
- auditory perceptual analysis
- Acoustic outcomes in vowels and speech- "we were away a year ago"
- Aerodynamic outcomes
- Patient perception of voice therapy questionnaire
- Exit interview about voice therapy

2. Upload a copy of all materials used to collect data about subjects: (Attach all surveys, interview/focus group scripts, and data collection forms except for case report forms, SCID or KSADS):

Document	Category	Date Modified	Document History
View Patient Perception of Voice Therapy Ziegler_2014.pdf(0.01)	Data Collection	1/16/2019	History
View Dev and Valid of VHI-10 Rosen_et_al-2004-The_Laryngoscope.pdf(0.01)	Data Collection	1/16/2019	History

3. * Will blood samples be obtained for research purposes?

Yes No

Consent Process

Enter N/A in response to the following questions if a Waiver of Consent is requested for all research activities or if no subjects are being enrolled.

1. * Indicate where the consent process will take place and at what point consent will be obtained:

Individuals identified as being eligible during the course of their clinical care visit at the University of Pittsburgh Voice Center will be informed of their eligibility by a co-investigator on this project. If the potential subject shows interest, a member of the research team, knowledgeable of the project will review the informed consent document with them and address any questions or concerns that arise. Potential subjects will be informed that their care at the Voice Center is not dependent on participation in this research, and that all research is voluntary. Potential subjects will also be informed that they do not have to decide to participate immediately. But we ask that they make the decision prior to receiving any voice therapy sessions so as not to confound the study results.

Ultimately, written informed consent will be obtained from the subject by a co-investigator.

2. * Describe the steps that will be taken to minimize coercion and undue influence, including assurance that there is sufficient time for subjects to make an informed decision:

Individuals will be permitted to take as much time as they need to decide. The only stipulation is that they may not have any "traditional" voice therapy sessions after determination of eligibility and enrolling into the study as this will confound the results.

3. For studies that involve multiple visits, describe the process to ensure ongoing consent:

4. * Steps to be taken to ensure the subjects' understanding:

Individuals identified as being eligible during the course of their clinical care visit at the University of Pittsburgh Voice Center will be informed of their eligibility by a co-investigator on this project. If the potential subject shows interest, a member of the research team, knowledgeable of the project will review the informed consent document with them and address any questions or concerns that arise. Potential subjects will be informed that their care at the Voice Center is not dependent on participation in this research, and that all research is voluntary. Potential subjects will also be informed that they do not have to decide to participate immediately. But we ask that they make the decision prior to receiving any voice therapy sessions so as not to confound the study results.

Ultimately, written informed consent will be obtained from the subject by a co-investigator.

5. *** Are you requesting an exception to the IRB policy related to the informed consent process:**

Yes No

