*** Will you be recruiting individuals for participation in this study?**

Yes No

1. * Describe who will be recruiting individuals for participation for this study:

Study team members also involved in clinical care.

2. * Select all methods to be used for recruitment:

Directly approaching potential subjects (in-person)

3. * Provide details on your recruitment methods:

Individuals will be identified during the course of usual clinical care of patients at the University of Pittsburgh Voice Center. As potential subjects are being clinically evaluated in the University of Pittsburgh Voice Center, they will encounter at least one member of the research team who will be able to determine eligibility through the clinical review of medical records associated with their visit. Once verification of eligibility is obtained, potential subjects will be approached by a member of the research team to review the informed consent document. Any and all questions will be addressed during this time.

4. * Describe all compensation/incentives offered to participants and timing of these offers:

Participants will be paid \$100 in total for completion of the 4 voice therapy sessions and follow-up session. The \$100 payment will be made after the completion of the 5 visits (4 therapy and 1 follow up). There will be no partial payment. Payment will be managed with a reloadable debit card.

Participants will be paid when they present for the follow-up visit after completing 4 voice therapy sessions.

5. Recruitment materials: (attach all material to be seen or heard by subjects, including advertisements and scripts)

Document Category Date Modified Document History

There are no items to display

Study Aims

1. * Describe the purpose, specific aims, or objectives and state the hypotheses to be tested:

To determine the efficacy of a semi-occluded mask in the treatment of patients with voice disorders

To determine initial efficacy of a semi-occluded facemask on voice outcomes in patients with MTD, lesions, and atrophy. We hypothesize that patients will demonstrate an improvement in acoustic, aerodynamic outcomes, and voice handicap index scores following therapy.

2. * Describe the relevant prior experience and gaps in current knowledge including preliminary data. Provide for the scientific or scholarly background for, rationale for, and significance of the research based on existing literature and how it will add to existing knowledge:

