Our group recently developed a semi-occluded facemask for use in patients with and without voice disorders. Recent preliminary results using this semi-occluded facemask indicated that the use of a certain mask port diameters may elicit voice with increased efficiency. A study of 5 participants without voice disorders revealed that a mask occlusion diameter of 6.4 and 3.2 mm resulted in improved vocal efficiency. A study of the immediate effects of a semi-occluded facemask in 20 patients with voice disorders revealed that occlusions diameters of 9.6, 6.4, and 3.2 mm all resulted in significant improvements in acoustic and aerodynamic voice outcomes.

The current study aims to expand upon these past studies by investigating the efficacy of use of a semi-occluded facemask in the treatment of patients with voice disorders.

Study Design

1. **Total number of subjects to be enrolled at this site (enter -1 for chart reviews, banking, registries):**

30

2. **Describe and explain the study design:**

Prospective, experimental

3. **Describe the primary and secondary study endpoints:**

4. **Provide a description of the following study timelines:**

Duration of an individual subject's active participation:

Approximately 6 weeks

Duration anticipated to enroll all subjects:

12-18 months

Estimated date for the investigator to complete this study (complete primary analyses):

12/31/2019

5. **List the inclusion criteria:**

males and females

age 18-60 years old

diagnosed by a multi-disciplinary team consisting of laryngologist and speech-language pathologist with muscle tension dysphonia (MTD) or vocal fold lesions deemed amenable to voice therapy (i.e. not surgical candidates)

6. **List the exclusion criteria:**

Age 61 or older (excluded due to differences in vocal fold tissue structure changes in this age and older)

Under 18 years of age

Current smoker (greater than 5 cigarettes/week)

7. **Will children or any gender, racial or ethnic subgroups be explicitly excluded from participation?**

Yes No

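### Convenience sampling by treating clinicians from the mask's own developer group lets eligible patients be passed over unrecorded; consecutive approach with a counts-only log looks feasible and cheap

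*Combined protocol and SAP*

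**What the plan says.** The sampling method is stated in Study Design, item 8: "Due to the pilot nature of the current study, we will use convenience sampling". The same item describes the source of patients: "Our clinic evaluates approximately 30 new patients each week", and "Behavioral voice disorders such as those included in the current research are approximately 60% of all new patient visits". It concludes that "we do not anticipate difficulty recruiting our target N of 20 for this pilot investigation". Study Design, item 1, gives 30 as the number to enrol, and item 4 expects enrolment to take 12 to 18 months.

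Recruitment Methods, item 1, names the recruiters: "Study team members also involved in clinical care". Item 3 says of potential subjects that "they will encounter at least one member of the research team who will be able to determine eligibility", and that they are approached once eligibility is verified. Consent Process, item 1, likewise has eligible individuals told of their eligibility by a co-investigator. Study Aims, item 2, says: "Our group recently developed a semi-occluded facemask for use in patients with and without voice disorders".

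The only analysis named is a paired t-test of VHI-10 against baseline (Study Design, item 8). There is no comparator. No section requires that every eligible patient be approached, sets an order of approach, or asks for a count of patients not approached or declining.

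**The concern.** In a single-group before-after study the mean change is the result. If the patients approached tend to be those expected to respond well, or those seen at a bad moment, the mean VHI-10 change moves directly, and no control group absorbs the shift. Three features make this worth guarding against here. The recruiters treat the patients and belong to the group that developed the device. One entry criterion, lesions deemed amenable to voice therapy, rests on clinical judgement. The number needed is small relative to the clinic's flow.

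Without a record of who was eligible and not enrolled, a reader of the result could neither rule selection out nor estimate it. Pilot status is the only reason given for the sampling method, yet the stated aim is initial efficacy and a significance test is planned.

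**Working it through.** **Plan's own figure.** The target of 20 (30 in Study Design, item 1) cannot be reproduced. No alpha, power, effect size or SD is given. Both values are carried through.

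**Flow.** Inputs: 30 new patients a week, 60% with behavioral voice disorders, and 12 to 18 months taken as 52 to 78 weeks.
- Weekly flow: 30 × 0.60 = 18.
- Total: 18 × 52 = 936 and 18 × 78 = 1,404.

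The 60% is a diagnostic class. It comes before the age, smoking and amenability criteria, willingness to attend the sessions, and consent.

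**Feasibility of consecutive enrolment.** The joint share (eligible and consenting) needed is N / flow:

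| N | 12 months | 18 months |
|---|---|---|
| 20 | 20/936 = 2.1% | 20/1,404 = 1.4% |
| 30 | 30/936 = 3.2% | 30/1,404 = 2.1% |

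Time needed is N / (18 × eligible share × consent share). The shares are not in the documents, so a range is assumed:

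| Eligible, consenting | Weeks, N = 20 | Weeks, N = 30 |
|---|---|---|
| 50%, 50% | 4.4 | 6.7 |
| 25%, 25% | 17.8 | 26.7 |
| 10%, 25% | 44.4 | 66.7 |
| 10%, 10% | 111 | 167 |

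Only the last row falls outside 78 weeks. In the third row, N = 30 needs more than 12 months but less than 18.

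**Possible bias (illustration on assumptions).** Let r be the correlation between the basis for selecting a patient and that patient's later VHI-10 change, and f the fraction of the available pool that is enrolled. If the top fraction f is taken and the variables are normal, the shift in mean change, in SD of change, is r × i(f), with i(f) = φ(z at 1 − f) / f. Neither r nor f is in the documents.

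| Scenario | f | i(f) | Shift, r = 0.1 to 0.2 |
|---|---|---|---|
| Three quarters of eligible, willing patients enrolled | 75% | 0.42 | 0.04 to 0.08 SD |
| Half enrolled | 50% | 0.80 | 0.08 to 0.16 SD |
| A quarter of the flow eligible and willing | 5.7% to 12.8% | 2.01 to 1.63 | 0.16 to 0.40 SD |
| Top selection from the whole flow (worst case) | 1.4% to 3.2% | 2.54 to 2.24 | 0.22 to 0.51 SD |

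The third row uses 20/351 = 5.7% and 30/234 = 12.8%, where 351 and 234 are a quarter of 1,404 and 936.

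**Against the test.** With two-sided 0.05 and 80% power (assumed), the paired t-test detects 0.66 SD at N = 20 and 0.53 SD at N = 30. If the true mean change were zero, the chance of a significant improvement would be 0.025 without selection. For N = 20 and r = 0.1 to 0.2, it becomes:
- about 0.04 to 0.055 if three quarters are enrolled;
- about 0.05 to 0.10 if half are enrolled;
- 0.17 to 0.19 at r = 0.1, and 0.53 to 0.58 at r = 0.2, in the worst case.

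**The case against.** The strongest reply is that the plan describes no picking. Recruitment Methods and Consent Process have eligibility checked at the visit and eligible patients then approached and informed. Item 8 asks for a sample-size justification, so convenience sampling there may only explain why N was not calculated. This stands as far as it goes: a reader might infer that clinicians hand-pick likely responders, and the documents do not support that. But neither section says that all eligible patients are approached, and the only sampling method named is convenience. If everyone is in fact approached, the proposed sentence merely records it.

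Second, a reader might infer that 20 to 30 are chosen from 936 to 1,404 candidates, or 1 in 31 to 1 in 70. That does not follow either. The raw diagnostic flow is not the eligible and willing pool. The plan's timeline implies 20/78 = 0.26 to 30/52 = 0.58 enrolments a week against a flow of 18, which suggests that eligible, willing patients or therapy places may be much scarcer. The worst-case shift is therefore an upper end, not an estimate. Patients also arrive one at a time and must consent, so taking the very top of the flow is not realistic.

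Third, Data Safety and Monitoring provides quarterly meetings that include recruitment. That is oversight, but it is neither an approach rule nor a log. An IRB form's silence is also weak evidence that no log is kept.

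Fourth, the document is dated February 2020 and gives 12/31/2019 as the estimated completion date, so enrolment may be far along. Its status is not stated.

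Finally, convenience sampling is ordinary in a pilot, and consecutive enrolment leaves regression to the mean untouched. Both are true, and they limit the weight of the point without removing it.

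**Conclusion.** The point holds as a cheap improvement to design and reporting. The plan permits selective approach by recruiters with an interest in the device, and it gives a reader no means of judging whether this occurred. It does not show that it occurred.

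The size cannot be fixed from the documents. At the assumed correlations it runs from negligible (0.04 SD, if most eligible, willing patients are enrolled) to close to the detectable effect (0.51 SD against 0.66 SD at N = 20, under top selection from the whole flow). The pilot label does not make convenience sampling necessary: consecutive enrolment fits the planned period unless fewer than about 1.4% to 3.2% of the diagnostic flow, depending on N and duration, is both eligible and consenting. The difference between 20 and 30 does not change this conclusion.

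**What to change.** In Study Design, item 8, replace the convenience-sampling statement with: *Every patient meeting the criteria is approached in order of clinic date until the target is reached, pausing only when no therapy slot is available.* Keep a counts-only log (eligible, approached, consented, reason not enrolled) and report that flow with the result.

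The cost is a little clerical time and less freedom over whom to approach. The time falls on clinicians as well as the coordinator: the Study Team Members table lists the coordinator as not involved in consent, so reasons for non-enrolment must come from those who see the patient. No extra patients or visits are needed. If enrolment has already closed, the approach rule comes too late, and what remains is to report whatever flow counts exist.

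The change limits selection by recruiters only. Regression to the mean, natural course and the lack of a control group remain, and the result should be interpreted with that in mind.

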*** Provide a justification and describe the qualifications of the individuals who will obtain consent:**

For this project, the PI and the Co-investigators have appropriate expertise and experience to enable them to appropriately discuss the study with participants and obtain consent.

Consent Forms

1. Consent Forms:

Document	Category	Date Modified	Document History
View Facemask consent PittPRO conv 2019.docx(0.03)	Consent Form	2/8/2019	History

Refer to the following templates and instructional documents:

- Guidance - Consent Wording
- Template - Consent Document - Short Form
- HRP-090 - SOP - Informed Consent Process for Research
- HRP-091 - SOP - Written Documentation of Consent

Medical Records

1. You are required to submit this study to the Research Informatics Office, Health Record Research Request (R3). Per UPMC Policy HS-RS0005, all research projects that access or involve UPMC electronic protected health information (e-PHI) must be submitted to R3, with the exception of clinical trials that are contracted through the UPMC Office of Sponsored Programs and Research Support (OSPARS).

Complete the R3 intake form available at <http://rio.pitt.edu/services>. An R3 representative will conduct a review. You will be notified once your R3 review is complete or if anything further is needed.

*** Describe the protected health information that will be collected from the covered entity and/or the research derived information that will be placed into the medical records:**

Medical record information to be accessed for research purposes may include the information associated with the eligibility of subjects as well as their follow up visit information. This would include VHI-10 score, computerized voice testing as well as the clinical examination performed by the laryngologist at any time.

Electronic Data Management

* **Will only anonymous data be collected** (select **NO** if identifiers will be recorded at anytime during the conduct of the study)?

Yes No

Select **all identifiers** to be collected during any phase of the research including screening:

Name:		Internet Protocol (IP) Address:	
E-mail address:		Web Universal Resource Locators (URLs):	
Social security #:		Social security # (for Vincent payment only):	

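### The paired VHI-10 test starts from an undated usual-care chart score with no repeat at session 1, so any change before first mask use counts as improvement or worsening following therapy

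*Combined protocol and SAP*

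**What the plan says.** Study Design, item 8, names one analysis: "A paired t-test will be used to assess whether VHI-10 improved significantly from baseline". No comparison group is described.

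Research Activities, item 1, gives the source of the starting value: "Baseline data to be collected will be extracted from the medical record". The list that follows marks VHI-10, the auditory-perceptual analysis, the acoustic outcomes and the aerodynamic outcomes as usual-care measurements. VHI-10 appears at two time points only, baseline and follow-up. On timing of treatment, the same item says "Participants will be assigned to a voice therapist (SLP) and scheduled for 4 sessions", with a follow-up testing visit one week later.

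Three other places bear on when the baseline was taken:

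- Recruitment Methods, item 3, has patients identified while they are being evaluated in the clinic, with eligibility judged from the records of that visit. Consent Process, item 1, repeats this.
- Consent Process, item 1, also says "But we ask that they make the decision prior to receiving any voice therapy sessions so as not to confound the study results". Item 2 sets no deadline for the decision and bars traditional voice therapy after eligibility and enrollment.
- Study Design, item 4, puts active participation at about 6 weeks, without saying when that period begins.

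**The concern.** A paired test from a chart score measures everything that happened between that score and follow-up. The part before session 1 cannot be due to the mask or to the therapy sessions, yet it carries full weight. Improvement over the wait would be credited to therapy, and worsening would hide benefit.

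The plan shows awareness of the general problem. It asks patients to decide before any voice therapy and bars traditional therapy, both in order to avoid confounding. Those safeguards deal with one cause of early change, other therapy. They do not deal with natural course or with other care during the wait. Because this test is the only analysis named for judging initial efficacy, its starting point deserves to be fixed.

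**Working it through.** **No figure to reproduce.** The target of 20 (Study Design, item 8) rests on convenience sampling, and item 1 gives 30 for enrollment. No alpha, effect size or SD of change is stated. Both values of N are carried below.

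**Step 1: decomposition.** For each patient,

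(follow-up − chart) = (session 1 − chart) + (follow-up − session 1).

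This is an identity. The mean of the first bracket enters the estimate one for one, with its own sign. A session-1 baseline removes that bracket and leaves the second untouched.

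**Step 2: assumptions for illustration.** None of these comes from the documents, except the 6 weeks and the two values of N.

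- Two-sided alpha 0.05, so the nominal chance of a significant improvement is 2.5%.
- No therapy effect.
- Untreated improvement b = 0.02 SD of the paired differences per week.
- SD of the paired differences the same for either baseline.

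**Step 3: formula.** With d the mean untreated change in SD units, the chance of a significant improvement is P(T > t(0.975, N−1)), where T is noncentral t with N−1 degrees of freedom and noncentrality d√N. The critical values are 2.093 (N=20) and 2.045 (N=30).

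**Step 4: results.** The 6 weeks can be read in two ways, because its start is not stated.

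| Reading | Baseline | d | N=20 | N=30 |
|---|---|---|---|---|
| Wait inside the 6 weeks | Chart | 0.02 × 6 = 0.12 | 7.4% | 9.3% |
| same, 1-week wait | Session 1 | 0.02 × 5 = 0.10 | 6.2% | 7.6% |
| same, 2-week wait | Session 1 | 0.02 × 4 = 0.08 | 5.3% | 6.2% |
| 4-week wait before the 6 weeks | Chart | 0.02 × 10 = 0.20 | 13% | 18% |
| same | Session 1 | 0.02 × 6 = 0.12 | 7% | 9% |
| No drift | Either | 0 | 2.5% | 2.5% |

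With a short wait inside the 6 weeks, the session-1 baseline gains about 1 to 3 percentage points. With 4 weeks beforehand it gains about 6 (N=20) or 9 (N=30). At a constant rate, the share of untreated change that it removes is wait ÷ total time: 1/6 = 17%, 2/6 = 33% and 4/10 = 40% in the three cases.

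**Step 5: the other direction.** Take a therapy effect that gives 80% power: 0.66 SD at N=20 or 0.53 SD at N=30. Worsening of 0.1 SD before session 1 lowers power to 66% (N=20) or 62% (N=30). The 0.1 SD is again an assumption.

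**The case against.** The strongest reply is that the baseline is probably recent. Patients are identified at a clinic evaluation, eligibility is read from that visit's records, and feasibility is argued from new-patient visits. The natural reading is that the score comes from that evaluation, with therapy following soon after. This largely stands. It makes a small bias plausible, but it does not turn a likely reading into a rule, and it leaves the time from evaluation to session 1 unlimited.

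It can also be said that naming the evaluation-visit score and recording its date would close the documentation gap without a new assessment. That is true of the documentation, but it would leave the pre-therapy change in the estimate.

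A third reply is that, without a control group, the repair is partial. That stands in full, as the shares in Step 4 show.

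A reader might go further than the documents allow in three ways:

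- **Very old scores or long delays.** Medical Records, item 1, says "This would include VHI-10 score, computerized voice testing as well as the clinical examination performed by the laryngologist at any time", but the closing words may attach only to the clinical examination. Research Activities says "All recruitment and enrollment will take place at UPMC Mercy. Voice therapy sessions will occur at Mercy, East, and Passavant and Bethel Park", but a change of site does not imply a delay.
- **Inflation by regression to the mean.** Entry is by diagnosis with no VHI-10 threshold, so elevated chart scores are not implied and no figure is offered for this.
- **Bias toward benefit.** The direction is unknown.

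**Conclusion.** The point holds as a gap in how the baseline is fixed. The paired test begins at a usual-care chart score whose visit, age and distance from session 1 are not specified, and no score is taken immediately before first mask use. That change before session 1 enters the estimate is certain by arithmetic. How much there is, and in which direction, is unknown and could be nothing.

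The figures above depend on the assumed 0.02 SD per week and on where the wait falls relative to the 6 weeks. They show a modest effect when the wait is short and a material one only when it is several weeks. The documents do not show that waits are that long, and they do not support a claim that the result will be inflated. This is a worthwhile, low-cost improvement to a pilot, not a flaw that invalidates it.

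**What to change.** Have each participant complete VHI-10 at session 1, before any mask use or therapy, and name that score as the baseline in the paired t-test. Keep the evaluation-visit score with its date, and report the days and the VHI-10 change from it to session 1 descriptively. Record dates and days to session 1 for the acoustic, aerodynamic and auditory-perceptual baselines as well, and state that those outcomes still start from the chart.

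State too that the session-1 score removes only change completed before session 1. Natural change from session 1 to follow-up remains, so the conclusion should stay at within-patient change following therapy, which is how the hypothesis is already framed.

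The cost is one 10-item questionnaire at a visit already planned, a few minutes per patient, and a short protocol modification. The VHI-10 baseline will be dated later than the other baselines. For anyone already past session 1, only the chart date and interval can be recovered. The estimated completion date (12/31/2019) precedes the document date (February 11, 2020), so how many participants could still benefit is unknown.
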